**EXECUTIVE SUMMARY**

Sponsor Name:	This is an Investigator Initiated Study being funded by OptiScan Biomedical Corporation.
Objectives:	
Assessment of glucose Time-in-Range (TIR) post implementation of the OptiScanner 5000 bedside glucose monitoring system (OptiScan Biomedical) in a Surgical ICU patient population.
 
Assessment of the time it takes the patient to achieve in range glucose values (using participant's clinical care defined glucose target range) while connected to the OptiScanner.

Clinical Hypothesis:	
Preventing glucose variability has been shown to be strongly associated with increased survival in non-diabetic critically ill adults (6-8). In clinical practice, it is very challenging to maintain critically ill patients' glucose values within a "target range" as the methods currently available to accomplish this are burdensome on the clinical care team and can be quite costly.
 
The primary endpoint of this study is to assess the level of TIR obtained in a surgical ICU patient population after implementing the OptiScanner 5000 glucose monitoring systems.

Name of Investigational Device(s):	
OptiScanner 5000 Glucose Monitoring System
 
FDA Cleared on October 16, 2017 (K162042). The device will be used without Clinical Laboratory Improvement Amendments (CLIA) oversight for this study.

Design:	Single center, non-randomized, study evaluating the proportion of patients maintaining in range glucose values (using participants' clinical care defined glucose target range) and the time it takes for patients to achieve in range glucose values in a Surgical ICU population after implementing the OptiScanner 5000 Glucose Monitoring system

Planned Enrollment:	
Enrollment into this trial will be in two phases. Phase One of the study will consist of study staff working with the clinical care team to operationalize the logistics involved with implementing the use of the OptiScanner. In addition, phase one subjects will provide the opportunity for the PI to observe the OptiScanner utility as a complement to the current glucose management of the patient. The continuous glucose monitoring provided by the OptiScanner may introduce additional glucose measurement information that would not have been known if it occurred between the routine clinical care glucose measurements and the clinical care team will be advised to confirm any OptiScanner glucose value (using routine clinical care methods) before making any modifications to patients' clinical care based on the OptiScanner glucose result. A research team member will be at the patient's bedside during his/her entire study participation to ensure that the clinical care team does not use the OptiScanner results independently to direct patient care and to observe how the additional glucose information is or is not used. A minimum of 50 patients will be enrolled in phase one.
 
Phase Two will commence after the data from phase one has been evaluated. The protocol will be updated with Phase Two procedures after the completion of the analysis of phase one results.
 
Study Completion:
 
 
• The study will be completed after enrolling 50 phase one evaluable subjects. An evaluable subject is defined as a subject with a minimum of 48 hours of OptiScanner monitoring.
 
						
Duration of Participation:	
Minimum of 48 hours of monitoring with the OptiScanner System
 
Maximum of 72 hours of monitoring with the OptiScanner System
						
Primary Endpoint:	
Time-in-range (TIR), post-OptiScanner system implementation:
 
 
 Target TIR		Primary Endpoint Evaluation of TIR	
 
 According to participants' clinical care defined target glucose range			
 
	Target TIR		Primary Endpoint Evaluation of TIR	According to participants' clinical care defined target glucose range		
Target TIR		Primary Endpoint Evaluation of TIR					
According to participants' clinical care defined target glucose range							
Secondary Endpoint	
Assessment of the time it takes the patient to achieve in range glucose values while connected to the OptiScanner.
						

Safety Endpoints:	The proportion of subjects that experience one or more Device Related Serious Adverse Events (DRSAEs).  Incidence of hypo/hyperglycemia
--------------------------	---

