### **3.2 Inclusion Criteria**

All subjects are required to meet the following inclusion criteria in order to be considered eligible for participation in this study:

1. Signed informed consent by the participant or his/her legally authorized representative;
2. At least 18 years old;
3. Admitted to a Surgical ICU or planned admission to a Surgical ICU at time of screening
4. Expected SICU stay of at least 48 hours at the time of enrollment
5. A vascular access device available for connection to the OptiScanner is either already in-place, or is planned to be placed with an expected usage of at least 48 hours.

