## **4.0 Study Design**

### **4.1 Study Design Description**

This is a Single-center, non-randomized, study evaluating the TIR in a Surgical ICU population after implementing the OptiScanner system.

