### **4.3 Study Endpoints and Other Assessments**

#### **4.3.1 Primary Endpoint**

The primary endpoint is an evaluation of the Glucose Time-in-range (TIR).

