#### **4.3.2 Additional Data Collected**

The following data will be collected during the OptiScanner evaluation:

- Demographic Data
- Date of admission
- Primary and secondary diagnosis
- History of thromboembolic events and clotting disorders
- Medications administered during ICU stay
- Insulin administration: timing, dosage, route and protocol used
- Insulin adjustment: reason for the adjustment, OS glucose value prior to insulin adjustment and standard of care confirmatory glucose value obtained if adjustment was related to an abnormal OS glucose value, timing of insulin adjustment, dosage, and route
- Dextrose administration/IV: timing, and dosage
- Dextrose adjustment: reason for the adjustment, OS glucose value prior to insulin adjustment and standard of care confirmatory glucose

value obtained if adjustment was related to an abnormal OS glucose value, timing of dextrose adjustment, dosage, and route

- TPN and other nutrition
- TPN and other nutrition adjustment
- Number of Hypoglycemic events (defined as glucose < 70 mg/dL)
- Number of Hyperglycemic events (defined as glucose > 200 mg/dL)
- Ventilator days, ICU LOS, and HLOS
- Infection outcome data
- Procedures including imaging, dialysis, and transfusions
- Date and time of OS connection/disconnect
- Contrast administration
- Discharge disposition (i.e. home, rehab, nursing home, death, etc.)
- Device related AE's and SAE's

Additional data not typically collected in the patient's medical records:

- Types and frequency of alarms (both dysglycemia and others) downloaded from the OptiScanner after the case
- The frequency of CVC maintenance incidents requiring disconnection from the OptiScanner system
- Comparator measurements (at the start, at approximately 24-hour intervals, and when prompted by the OptiScanner (i.e. cartridge change) Patients will have a study blood draw after OptiScanner connection, at approximately 24-hour intervals, and when prompted by the OptiScanner (i.e. cartridge change). The sample may be point of care or sent to the laboratory for analysis.
- History of CVC line (occlusions, other clotting disorders, age, etc)
- Clinical care team action/inaction details related to all glucose values (both OptiScanner and standard of care values).

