#### **5.0 Assessment of Time-in-Range (TIR)**

TIR is calculated as the number of points in range divided by the total number of measurements presented. When the smart alarm is active, readings during that period are excluded from the calculation.

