## **11.0 Data Handling and Record Keeping**

The Investigator must maintain detailed source documents on all subjects who are enrolled in the study. Source documents include medical records, hospital charts, clinic charts, Investigator study files, as well as the results of diagnostic tests (e.g., medication records, laboratory tests, hemodynamic studies).

The following minimum information should be entered into the subject's study and/or medical record:

- The date of enrollment and study ID
- The study protocol name and number
- Documented eligibility requirements (e.g., medical history, study procedures and/or evaluations)
- The duration of study participation
- Evidence that required evaluations were completed
- Use of any concurrent medications during study enrollment, and where infused
- Transfusions or Dialysis
- Documentation of specific device used
- Occurrence and status of any adverse events that in the Investigator's opinion are related to the OptiScanner
- All OptiScanner alarms
- The date the subject exited the study and a notation as to whether the subject completed the study or was discontinued, including the reason for discontinuation
- The insulin, dextrose, and nutrition administration delivery

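### Does the Design row's proportion of patients, together with an unlisted target range, leave the primary endpoint undefined?

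*Protocol*

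**What the plan says.** **Design row.** The Executive Summary describes a single-center, non-randomized study "evaluating the proportion of patients maintaining in range glucose values", plus the time patients take to come into range. It does not say what share of readings, or what duration, counts as maintaining.

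**Other statements of the main evaluation.** Section 4.1, the body counterpart of that row, describes a "study evaluating the TIR in a Surgical ICU population after implementing the OptiScanner system". The Clinical Hypothesis and Primary Endpoint rows of the Executive Summary, Section 2.0 and Section 4.3.1 also name TIR. Section 5.0 gives the formula: "TIR is calculated as the number of points in range divided by the total number of measurements presented", with readings taken while the smart alarm is active left out.

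**Range.** The target is set "According to participants' clinical care defined target glucose range". The nearest entry under Additional Data Collected is "Insulin administration: timing, dosage, route and protocol used". The nearest in the minimum record of Section 11.0 is "The insulin, dextrose, and nutrition administration delivery". Neither names the range.

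**Record length.** An evaluable subject has at least 48 hours of monitoring (Executive Summary, Planned Enrollment). Participation ends at discharge or at 72 hours (Section 4.5).

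**Use.** Section 7.0 plans no formal statistics for Phase One and uses its results to inform the Phase Two power analysis.

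**The concern.** Three things appear to leave the main result open.

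- A proportion of patients and a share of readings are different quantities. The first cannot be computed until maintaining is defined. A reader who sees only the Design row would expect a result that Section 5.0 does not produce.
- TIR depends on its limits. If a patient's range, or a change to it, goes unrecorded, the device's percent in range cannot readily be checked against the downloaded readings. The insulin protocol might imply a range for patients on insulin, but the criteria introduced by "All subjects are required to meet the following inclusion criteria" do not include insulin treatment.
- A patient who starts out of range will tend to show a lower TIR on a 48-hour record than on a 72-hour one.

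At stake is the Phase One TIR as an input to Phase Two. A mean TIR and a patient proportion would feed a power analysis differently.

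**Working it through.** The protocol gives no figure to reproduce: the 50 subjects rest on no stated alpha, power, effect or SD. The check is therefore mainly textual. The distributions below are assumptions used only to show size.

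**1. Which quantity is primary?**

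| Place | Quantity |
|---|---|
| Executive Summary, Design | proportion of patients, no cut-off |
| Executive Summary, Clinical Hypothesis | level of TIR, named as the primary endpoint |
| Executive Summary, Primary Endpoint | TIR |
| Section 2.0 | TIR |
| Section 4.1 | TIR |
| Section 4.3.1 | TIR |
| Section 5.0 | TIR, with formula |

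The Design row stands alone, and the Clinical Hypothesis row of the same summary contradicts it. It does not call its quantity an endpoint. The secondary endpoint (time to reach range) and the safety endpoints (device-related serious events, hypo/hyperglycemia) measure other things and do not use a patient proportion in range either. The only TIR cut-off in the protocol, above 80% in 70 to 140 mg/dL, is cited background in Section 1.1 and is not adopted.

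**2. What would the missing cut-off be worth if it were used?** Assume patient-level TIR follows a beta distribution with mean 0.60 and SD 0.20. Then a + b = 0.60 × 0.40 / 0.20² − 1 = 5, so a = 3 and b = 2. The share of patients above cut-off c is 1 − (4c³ − 3c⁴):

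- c = 0.5: 1 − 0.3125 = 68.7%
- c = 0.7: 1 − 0.6517 = 34.8%
- c = 0.8: 1 − 0.8192 = 18.1%

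Over means of 50% to 70% and SDs of 15 to 25 points, the 80% cut-off gives 1.9% to 44.7% and the 50% cut-off gives 50.0% to 89.2%. The spread is wide, but it belongs to an analysis that no section requests.

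**3. Can the range be obtained?** Section 8.0 makes the investigator responsible for developing the case report forms. Section 11.0 calls its list a minimum and makes medical records and hospital charts source documents. A range defined by clinical care would be expected there, though the protocol does not say so. Additional Data Collected also includes what the care team did or did not do about every glucose value, and Section 4.2.1 keeps a research team member at the bedside throughout connection.

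Size if a limit were wrong, assuming Normal glucose with mean 145 and SD 35 mg/dL: an upper limit of 180 set 10 too high moves TIR by P(180–190) = Φ(1.286) − Φ(1.000) = 0.901 − 0.841 = 5.9 points. With mean 130 and SD 25 it is Φ(2.4) − Φ(2.0) = 1.5 points. With mean 145 and SD 25, a limit of 140 set 10 too high moves it by 15.9 points.

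**4. Record length.** Let a patient be out of range for the first s hours and in range a share p of the time afterwards. Over L hours, TIR = (L − s)p / L. With s = 12:

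- p = 1.0: 36/48 = 75.0% against 60/72 = 83.3%, a gap of 8.3 points
- p = 0.6: 45.0% against 50.0%, a gap of 5.0 points

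With s = 4 the gaps are 2.8 and 1.7 points. The protocol gives no spell lengths and no distribution of record lengths. The quantity itself is well defined, because Section 5.0 takes all readings presented outside smart-alarm periods. The slow start is described separately by the secondary endpoint.

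**The case for a change.** The strongest argument for acting concerns the range. It must be captured while care is given; rebuilding limits and their change times from charts afterwards is less certain, and one extra field costs almost nothing. The data list is protocol content and goes into such detail as line history and alarm types, so leaving out the one item on which the primary endpoint depends is a fair thing to notice. Section 8.0 says that the device calculates percent in range but not with which limits.

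This much stands: the range is not expressly listed, and naming it would be a sensible clarification. It does not follow that the endpoint cannot be scored or checked. The endpoint is defined by that range, so whoever builds the forms under Section 8.0 has to obtain it. The two lists do not prevent this.

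On the Design row, it can be argued that a protocol naming two quantities cannot have both served by one analysis plan. That would carry weight if the two had equal standing. Here one summary phrase faces the stated primary endpoint, its formula and the body's own design description.

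On Phase Two, its procedures are still to be written (Section 4.2.2). Glucose readings are stored and downloaded (Section 8.0), so once the ranges are in hand a mean TIR, a patient proportion or a first-48-hour TIR can be tabulated if Phase Two needs it.

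**Conclusion.** The observations are accurate, but no change to the plan follows. The Design row is a clerical looseness: aligning it with Sections 4.1 and 5.0 would tidy the summary and alter no result. The unlisted range is a gap that the investigator and analyst fill in the ordinary course of scoring the endpoint. Record length shows nothing wrong, since the full record is what Section 5.0 prescribes, and a first-48-hour figure would be an optional extra tabulation.

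The sizes above (18% to 69% across cut-offs, 1.5 to 15.9 points for a misplaced upper limit, 1.7 to 8.3 points for record length) all rest on assumed distributions or spells. They show what could happen under choices the protocol does not make. No stated number, error rate or sample size is wrong, and Phase One is descriptive. The conclusion rests on two assumptions: that care-defined ranges are documented in the clinical record, and that the case report forms capture what the primary endpoint needs.

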## 1.0 Introduction

### 1.1 Background and Rationale

Hyperglycemia [1-4], hypoglycemia [1,5] and glycemic variability [6-8] are independently associated with morbidity and mortality of critically ill patients. Blood glucose control with insulin has the potential to decrease morbidity and mortality of intensive care unit (ICU) patients. Blood glucose control with insulin, however, is associated with an increased risk of hypoglycemia and may not decrease glycemic variability. In addition, blood glucose control with insulin utilizing manual systems for glucose measurement is blood-consuming and time-consuming, since frequent blood draws for glucose measurements are necessary in order to achieve blood glucose control.

Severe hypoglycemia (blood glucose level < 40 mg/dl) is a feared complication of blood glucose control with insulin. Undoubtedly, with the implementation of blood glucose control with insulin the incidence of hypoglycemia increases [9-15]. Several reports showed a significant association between hypoglycemia and patient outcomes [1,5,8,16]. Recently, an association has even been suggested between moderate hypoglycemia (blood glucose level between 40–69 mg/dL) and patient outcomes. Incidences of moderate hypoglycemia are more prevalent than severe hypoglycemia. The risk of developing (severe or moderate) hypoglycemia hampers, at least in part, broad implementation of blood glucose control with insulin, in particular when aiming at normal blood glucose levels, such as 80 – 150 mg/dl [17,18].

Recent studies showed significant associations between glycemic variability and patient outcomes [6-8,19,20]. Krinsley, et al, demonstrated that a TIR of 70 to 140 mg/dl > 80% was strongly associated with survival in critically ill patients without diabetes, independent of ICU LOS or severity of illness [21].

Implementation strategies of blood glucose control have mostly been accomplished with manually operated portable whole blood glucose meters, which suffer from a variety of error sources that can put intensively managed patients at risk for insulin

over- and/or under-dosing [23]. Furthermore, all manually operated whole blood glucose monitoring measurement devices lack trending, though immediate feedback and predictability of the effects of insulin infusions are highly needed when infusing insulin in critically ill patients [24]. In addition, each blood glucose measurement not using a finger stick requires a substantial volume of blood and is time-consuming [25].

Automated, frequent, plasma-based glucose monitoring with the OptiScanner 5000 glucose monitoring system has the potential to improve a patient's glucose TIR by improving all 3 domains of glycemic control: reducing hyperglycemia while at the same time preventing hypoglycemia and reducing glycemic variability. Second, it could reduce the workloads associated with the high number of blood samples to be obtained and analyzed [22,26-29].

## 1.2 Device Description

The OptiScanner® 5000 Glucose Monitoring System from OptiScan Biomedical Corporation is an automated, bedside glucose monitoring system designed to quantitatively measure the concentration of venous blood glucose. When attached to a patient, the OptiScanner® 5000 Glucose Monitoring System automatically draws a 3 mL blood sample, retains a micro-sample of blood for analysis (0.17 mL), and returns the remaining portion of the blood to the patient. The OptiScanner® 5000 Glucose Monitoring System analyzes the retained portion of the blood sample and then displays a glucose value. The OptiScanner® 5000 Glucose Monitoring System provides trending glucose information, which allows for decision-making based on a trend rather than any single glucose value.

The OptiScanner automatically performs the following functions as part of its monitoring cycle:

- Draws blood from the patient.
- From the blood withdrawn, retains a micro-sample (0.17 mL) blood sample for glucose measurement.
- Returns the unused blood to the patient along with a small (2.5 mL) amount of saline solution.
- Spins the blood sample, separating plasma from red blood cells.
- Measures optical signals from the plasma sample using a mid-infrared spectrometer.
- Adjusts for interfering substances, referencing a proprietary measurement algorithm.
- Calculates the latest blood glucose value, displays it on-screen, and updates the trending graph with patient's real-time glucose information.

## GIDE Protocol – FINAL (Rev D) October 8, 2018

[figure not shown]
The OptiScanner disposable cartridge is the sterile container within which the blood sample is prepared and analyzed. The Cartridge is for single patient use only. A new sterile Cartridge must be used for each new patient. In normal usage, the Cartridge will last for up to three days (72 hours) of monitoring.

The connection between the OptiScanner and the patient is accomplished through a vascular access device. Vascular access devices for OptiScanner connection include Central Venous Catheters (CVC) and Multi-lumen Access Catheters (MAC). The OptiScanner patient connector design employs a standard universal luer connector and can be successfully used with these devices. The type of device selected and its placement on the subject shall be determined by the user. Placement of the vascular access device is performed in accordance with the vascular access devices instructions for use but must be connected to the venous side. The OptiScanner must be connected to the most proximal port of the CVC or MAC.

[figure not shown]
The OptiScanner is composed of three main components (see Figure 1 and 2):

- OptiScanner Instrument with integrated pump, spectrometer, and user interface
- OptiScanner Transport Cart with a single IV pole or double IV poles (Cart)
- OptiScanner Disposable Cartridge (Cartridge)

**Figure 1:** Instrument mounted on the transport cart (up to two poles may be assembled)

**Figure 2:** Disposable device

### **1.3 Indications For Use**

The OptiScanner® 5000 Glucose Monitoring System is an automated, bedside glucose monitoring device indicated for detecting trends and tracking patterns in persons (age 18 and older) in the surgical intensive care unit. The system collects a venous whole blood sample via connection to a central venous catheter, centrifuges the sample, and measures the plasma glucose concentration. It is not intended for the screening or diagnosis of diabetes mellitus but is indicated for use in determining dysglycemia. The OptiScanner® 5000 Glucose Monitoring System is for in vitro diagnostic use.

### **1.4 Regulatory Status**

The OptiScanner 5000 Glucose Monitoring System was FDA-Cleared for commercialization in the USA on October 16, 2017 (K162042) however this device is not currently commercially available in the US.

